## **Primary Safety Outcome Measure**

The primary safety outcome measures will be the total number of and percentage of patients with major peri-PCI procedure adverse events, such as hypotension, angina, myocardial ischemia, myocardial infarction (if the patient is determined to have had unstable angina rather than non-ST-elevation MI at admission), cerebrovascular event (CVA), vermicular tachycardia, bleeding (at the PCI access and apheresis cannulation sites in the apheresis patients and at the PCI access site in the non-apheresis control patients), and death. The peri-PCI procedure is defined as encompassing the time of the PCI procedure and the time of the subsequent LDL-apheresis procedure for ILLT group versus the time of the PCI procedure for SMT group. All LDL-apheresis-related adverse events in the ILLT group, including any minor expected events, will be recorded.

## **Secondary Safety Outcome Measure**

The secondary safety outcome measures will be the total number of and percentage of patients with statin-related abnormal liver function test events and statin-related muscle injury events, which could occur due to the maximum dose of statin drugs being given to both the ILLT group and SMT group patients. The statin-related muscle injury is defined as a muscle injury which cannot be attributed to a non-statin cause and which is evidenced by symptoms (muscle soreness, pain, or tenderness) and/or lab tests such as serum total creatine phosphokinase (CPK), CPK-MM, or myoglobin.

## **Primary Effectiveness Outcome Measure**

The primary effectiveness outcome measure will be the change in the total atheroma volume within a  $\geq 20$  mm long segment of the target coronary artery from baseline to 12 weeks post-PCI. The measurement will be done via IVUS-VH at 2 time points (baseline during index PCI and 90-day follow-up).

## **Secondary Effectiveness Outcome Measures**

The secondary effectiveness outcome measures will include:

1. The %NC component of atheroma. The %NC component of atheroma will be obtained via IVUS-VH at 2 time points (baseline during index PCI and 90-day follow-up).
2. EPC-CFU/ml of peripheral blood. The cell culture assay and quantification of circulating EPC-CFU will be performed for patients recruited at the Dallas VA center only. The assay will be done at 4 time points (pre-PCI, post-PCI, 30-day follow-up, and 90-day follow-up).

3. The major adverse cardiovascular endpoints (MACE) including death, myocardial infarction, coronary revascularization, and stroke during the follow-up periods. The major adverse CV events will be collected via both clinical visits for up to 6 months post-PCI and searches of the VA Austin database for up to 1 year post-PCI. Approvals for using the patients' Social Security Numbers for data searching will be obtained via informed consent form.

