This is the second phase of a multi-center trial of ACS patients. The first phase was a safety study involving 31 patients and was completed in December 2012. US Food and Drug Administration (FDA) reviewed the safety and efficacy data from the first phase and approved proceeding to this phase. In this trial, 128 participants will be randomized in a 1:1 ratio to either initial LDL-apheresis and an oral daily dose of 40-80mg of Atorvastatin or equivalent (ILLT group) vs. a daily dose of 40-80mg of Atorvastatin or equivalent without LDL-apheresis (SMT group) following an uncomplicated PCI. Intravascular ultrasound with virtual histology (IVUS-VH) derived coronary atheroma volume and composition will be obtained at baseline and 90 days after enrollment, while peripheral blood sampling will be performed at enrollment, and at 24 hours, 30 days, and 90 days post-PCI, along with a four-month and a six-month clinical follow-up visits to determine whether the ILLT group will affect:

1. The total number of and percentage of patients with major peri-PCI procedure adverse events (primary safety endpoint)

2. The total number of and percentage of patients with statin-related abnormal liver function test events and statin-related muscle injury events (secondary safety endpoint)
3. The total atheroma volume within a ≥ 20 mm long segment of the target coronary artery at 90 days IVUS-VH follow-up (primary effectiveness endpoint)
4. The %NC component within a ≥ 20 mm long segment of the target coronary artery at 90 days IVUS-VH follow-up (secondary effectiveness endpoint)
5. The EPC-CFU/ml of peripheral blood, compared to SMT group from baseline to 30 days and 90 days post-PCI (secondary effectiveness endpoint)
6. The major adverse CV events (MACE) at 90 days and at six months follow-up (secondary effectiveness endpoint)

2. Background and Significance

2(a) Background

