The primary effectiveness outcome measure will be the change in the total atheroma volume within a ≥ 20 mm long segment of the target coronary artery from baseline to 90 days post-PCI. The measurement will be done via IVUS-VH at both centers of investigation.

[figure not shown]
The secondary effectiveness outcome measures will include the %NC component of atheroma, EPC-CFU/ml of peripheral blood, and major adverse cardiovascular endpoints (MACE) including death, myocardial infarction, coronary revascularization, and stroke during the follow-up periods. The cell culture assay and quantification of circulating EPC-CFU will be done for patients recruited at the Dallas VA center. The major adverse CV events will be collected via both clinical visit and searches of the Austin database for VA hospital utilization by Hines staff. Approvals for using the patients' Social Security numbers for data searching will be obtained.

4(c) Study Design and Procedures

The proposed study is a multi-center, randomized controlled study comparing atheroma volume, %NC component, and peripherally circulating EPC-CFU/ml of blood in ILLT vs. SMT groups of ACS patients undergoing PCI (**Figure 7**). All patients will sign an informed consent during the index hospital admission for ACS but prior to any study-

related procedure. The protocol will be approved by each site's institutional review board.

Figure 7: Study design overview for primary endpoint:

4(c)(i). Subject Screening Criteria (Figure 7, green arrow): Patients presenting with an ACS, LDL ≥ 70 mg/dl on Atorvastatin ≤ 80 mg or equivalent dose of another statin, normal liver function test (LFT) and referred for non-emergent cardiac catheterization (the procedure is not required to be performed within 3 hours after patient presentation) will be screened and consented during the index hospital admission for ACS. Patients on ACE inhibitors will either have it discontinued or switched to an angiotensin receptor blocking agent (ARB). All screen eligible patients will be subsequently asked to sign an IRB-approved informed consent form prior to clinically indicated PCI or any subsequent study related tests.

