4(c)(v)(2). Randomization and Blinding Procedures: Following an uncomplicated PCI procedure, patients who are eligible and willing to participate in the study will be randomly assigned to either the ILLT or SMT arm using an automated telephone-based randomization system. A touch-tone phone is necessary to use this Voice Information System (VIS) to randomize eligible subjects. CSPCC will assign each site a unique 6-digit PIN that the unblinded staff can use to access the VIS system and randomize a subject (or add/update an SSN). The VIS will query the unblinded staff for subject information and confirm these data prior to determining the subject's treatment group assignment. A copy of the appropriately executed consent and HIPAA authorization documents must be on file at the Hines CSPCC within 24 hours of randomization. If the VIS is not working during normal business hours, the research coordinator can telephone the Hines CSPCC staff to randomize a patient. The subjects or Site Investigators will not be blinded to the study treatment assignment; however all follow-up visits and endpoint adjudications will be performed by a dedicated study nurse blinded to treatment allocation. Patients will be cautioned not to reveal his/her treatment allocation to the blinded study nurse. This blinding precaution will be emphasized by the

procedures written into the study Operations Manual and the communications to the Site Investigator, the Site Coordinator and other study personnel during the kick-off meeting and the teleconference calls throughout the study. Patients will be screened and consented before PCI, but will have the opportunity, after PCI, to decline participation in the study and will not be randomized if they choose not to participate.

4(d) Intervention and Treatment

The randomized treatment regimens of this study include:

- (i) ILLT
- (ii) SMT

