All study patients will undergo IVUS-VH analysis at index PCI and at follow-up. A minimum distance of 10mm away from the PCI site is the preferred site to visualize the atheroma volume with IVUS-VH. Patients will return at 90 days from index PCI for repeat cardiac catheterization and ≥ 20 mm matched target coronary artery segment IVUS-VH at the exact same site as that of baseline using similar projections and side branch and/or calcification reference (**Figure 5**) using the technique published by our group²⁹. A core laboratory consisting of two experienced cardiologists blinded to the study treatment allocation will review baseline and follow-up coronary arteriograms and IVUS-VH of each patient in the study. These two cardiologists will be independent and have no direct relationship to the study team. If any disagreement occurs between these two cardiologists regarding the angiogram or IVUS-VH interpretation, a third cardiologist will be referred to review the data and break the tie. After visual evaluation, quantitative analysis (QCA) will be performed using a standard automated edge-detection method. Angiographic restenosis is defined as $\geq 50\%$ reduction in minimum luminal diameter (MLD) of the intervened segment during index PCI.

Figure 8: PREMIER study timelines

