All adverse event, serious adverse event and MACE assessments during follow-up will be performed during patient interviews or history and physical assessments and phone interviews, as indicated in Table 1.

Figure 9: Schematic (A) and on-line in vivo (B) IVUS-VH coronary analysis

[figure not shown]

Table 1: Follow-up study visits, clinical and laboratory testing schedule

Visits (days)*	H&P	EKG	Card. cath./IVUS-VH	FL	BMP + LFT	CBC	EPC	Phone Call
Screening/Recruitment	+	+		+	+	+		
Pre-PCI							+	
Index PCI			+					
Post-PCI		+		+	+	+	+	
Hospital Discharge following index PCI for ACS								
30-day f/u visit	+	+		+	+	+	+	
60-day f/u visit								+
90-day f/u IVUS-VH	+	+	+	+	+	+	+	
4-month f/u visit	+	+		+	+	+		
6-month f/u visit	+	+		+	+	+		

*These tests will be performed on all patients in study with “+” indicated when the tests are performed. All follow-up visits calculated from the day of study treatment randomization (dark gray line). Follow-up visits to be scheduled within ± 7 days of that time point in study. 90-day follow-up only to be scheduled ± 15 days of the 90-day time point.
 
H&P=history and physical; EKG=electrocardiogram; Card. cath./IVUS-VH=cardiac catheterization/PCI/intravascular ultrasound with virtual histology; FL=fasting lipids; BMP=basic metabolic profile; LFT=liver function test; CBC=complete blood count; EPC=endothelial progenitor cell; PCI=percutaneous coronary intervention; ACS=acute coronary syndrome; f/u=follow-up.
								

4(f) Adverse Event (AE) and Serious Adverse Event (SAE) Assessments and Reporting

- 4(f)(i). Role of the Local Site Investigator in Adverse Event Monitoring: The local Site Investigator will be responsible for following adverse event reporting requirements:
- (1). Reviewing the accuracy and completeness of all adverse events reported
 - (2). Complying with study policies as well as local IRB policies for reporting serious adverse events or problems involving risks to subjects or others in VA research.

- (3). Reporting to the IRB any safety issues reported to the site by the Sponsor (Study Chair), and
- (4). Closely monitoring of study participants for any new Adverse Events (AE), Unanticipated Adverse Device Effects (UADE), or Serious Adverse Events (SAE).

4(f)(ii). Definitions:

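### MACE counts every coronary revascularisation, including procedures prompted only by the 90-day catheterisation that the protocol requires of all patients

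*SAP*

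**What the plan says.** **Definition.** SAP, Secondary Effectiveness Outcome Measures, item 3: "The major adverse cardiovascular endpoints (MACE) including death, myocardial infarction, coronary revascularization, and stroke during the follow-up periods". Protocol 4(b) matches: "major adverse cardiovascular endpoints (MACE) including death, myocardial infarction, coronary revascularization, and stroke during the follow-up periods". The analysis sections (Protocol 4(g)(vi); SAP, Analysis of Secondary Effectiveness Outcomes) repeat the four components. None of these places sets a symptom or ischaemia criterion or separates procedures by trigger.

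**Time points.** Protocol 1(c), objective 6: "The major adverse CV events (MACE) at 90 days and at six months follow-up". Protocol 4(a) names the same two.

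**Mandated catheterisation.** Protocol 4(e): "Patients will return at 90 days from index PCI for repeat cardiac catheterization". The Table 1 footnote gives the window: "90-day follow-up only to be scheduled ± 15 days of the 90-day time point". That footnote counts visits from randomisation, whereas 4(e) counts from index PCI. Under 4(e), a clinically indicated catheterisation within two months of the scheduled one takes its place.

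**Blinding.** Protocol 4(c)(v)(2): "The subjects or Site Investigators will not be blinded to the study treatment assignment". The same sentence goes on to say that "all follow-up visits and endpoint adjudications will be performed by a dedicated study nurse blinded to treatment allocation". Protocol 4(e) adds "A core laboratory consisting of two experienced cardiologists blinded to the study treatment allocation" for image review, and 4(f)(iv) sets up a Clinical Events Committee (CEC), independent of the Study Chair and Site Investigators, for adverse events.

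**The concern.** Revascularisation is the one MACE component that a study procedure can itself bring about. A patient without symptoms is catheterised because the protocol asks for it, a lesion is seen and treated, and the patient becomes a MACE case. Without the study visit that event might not have occurred. It says little about whether apheresis lowers clinical risk, which Protocol 4(a) names as an aim when it expects fewer early events.

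The planned analyses (chi-square, mean cumulative function, time to first MACE) would all absorb a cluster of procedures around the mandated visit. A 90-day count is the most exposed, because that visit may fall on either side of day 90.

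**Working it through.** **1. The plan's own figure.** There is none for MACE: no rate, effect or power is stated. The sample size of 128 is for atheroma change. A two-sample t-test with d = 0.65, two-sided 5% and 90% power needs 51 per arm, so 102 in total, and 102 / 0.80 = 127.5, or 128. It reproduces, but is used here only for the 64 per arm and the 20% drop-out.

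**2. Do the safeguards close the gap?**

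| Safeguard | What it protects | Removes angiogram-prompted procedures? |
|---|---|---|
| Blinded study nurse, 4(c)(v)(2) | Event classification | No; the definition includes them |
| Blinded core laboratory, 4(e) | Image reading | No; it reviews films |
| CEC, 4(f)(iv) | Adverse event adjudication | No; no revascularisation criteria are given |

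Faultless adjudication against an unqualified definition still counts every procedure.

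**3. Number of procedures (assumed rate).** Attendees: 128 x 0.80 = 102.4. At 3%: 102.4 x 0.03 = 3.1. At 10%: 102.4 x 0.10 = 10.2. For scale, an assumed background MACE rate of 5-10% gives 128 x 0.05 = 6.4 to 128 x 0.10 = 12.8 patients. The 28.8% recurrent-event rate in Protocol 2(a)(ii), whose time horizon is not stated there, would give 128 x 0.288 = 36.9.

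**4. Equal thresholds by arm.** Let p be the MACE risk without prompted procedures and r the prompted fraction among attendees who are otherwise event-free. The observed risk is p + (1 - p) x 0.8r. Take p = 10% in SMT and 5% in ILLT, a true risk ratio of 0.50 (assumed):

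| r | SMT | ILLT | Risk ratio |
|---|---|---|---|
| 3% | 0.10 + 0.90 x 0.024 = 0.122 | 0.05 + 0.95 x 0.024 = 0.073 | 0.60 |
| 5% | 0.10 + 0.90 x 0.04 = 0.136 | 0.05 + 0.95 x 0.04 = 0.088 | 0.65 |
| 10% | 0.10 + 0.90 x 0.08 = 0.172 | 0.05 + 0.95 x 0.08 = 0.126 | 0.73 |

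Chi-square power at 64 per arm is 19% without prompted procedures, 14% at r = 5% and 11% at r = 10%. With 28.8% against 14.4%, the risk ratio moves from 0.50 to 0.56 (r = 5%) and 0.62 (r = 10%), and power falls from 51% to 44% and 39%.

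With no true effect and equal r, exact enumeration of the chi-square test gives rejection rates of 4.8-5.1%, so false positives are not inflated.

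**5. Unequal thresholds by arm (hypothetical).** With no true effect, r = 10% in SMT and 5% in ILLT, the rejection rate is 8% at a base risk of 10% and about 11% at a base risk of 5%.

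**6. The 90-day boundary.** 90 - 15 = 75 and 90 + 15 = 105, so 31 days are permitted. Days 75 to 90 are 16 (16/31 = 52%) and days 91 to 105 are 15 (48%). Under a fixed day-90 cut, a procedure done at the study visit is counted or not according to the visit date. All 31 days lie within six months, so the six-month total does not change.

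**The case against.** **Blinding is stronger than open label suggests.** This is true: a blinded nurse adjudicates, the core laboratory is blinded and the CEC is independent of the investigators. A reader might infer that unblinded operators decide these procedures and so bias MACE by arm. The documents do not support that inference. They leave Site Investigators unblinded and name no blinded 90-day operator, but they do not say who decides on revascularisation at that visit or whether that person knows the arm. Both arms have the same angiogram on the same schedule, and equal thresholds give dilution (step 4).

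**The added procedures need not dominate.** This also stands. Three to ten are comparable with a 5-10% background, but small beside the roughly 37 patients implied by 28.8%. Every rate here except the 28.8% is assumed.

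**The day-90 cut is a reading.** The SAP refers only to the follow-up periods, and the protocol wording could mean events up to the 90-day visit. On that reading the scheduling problem takes another form: the period itself runs for 75 to 105 days. Either way the plan needs a rule.

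**MACE is secondary and unpowered.** Agreed. At 10% against 5%, power is only 19% even with a clean definition. Event definitions may also sit in the operations manual or case report forms, which are not among these documents. That limits the weight of the point, but MACE is a named effectiveness objective and the correction is cheap.

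**Conclusion.** The point holds as a matter of endpoint definition. As written, the plan mixes procedures prompted by its own 90-day angiogram into a stated secondary effectiveness outcome, and the blinding measures do not separate them.

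- **Size:** about 3 to 10 procedures, assuming 3-10% of about 102 attendees; the documents give no rate.
- **Effect with equal thresholds:** dilution. In the 10% against 5% illustration, a true risk ratio of 0.50 appears as 0.60 to 0.73.
- **Bias by arm:** not shown. It is conditional on treatment thresholds that differ by arm.
- **Timing:** 16 permitted visit days against 15, only if 90-day MACE is read as a fixed day-90 cut. That about half of the prompted procedures would miss the count is a further inference, which needs visits spread evenly over the window. The six-month total is unaffected.

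The primary endpoint is not touched. This is a worthwhile, low-cost improvement and does not threaten the trial's main conclusion.

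**What to change.** In Protocol 4(b) and the SAP's secondary outcome section:

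1. Count in MACE only revascularisation driven by symptoms or documented ischaemia, under criteria fixed in advance and classified blind to arm through the existing blinded adjudication.
2. Record the reason for each procedure on the case report form. For events found only in the database search, take it from the records.
3. Report procedures prompted only by the protocol angiogram separately, by arm.
4. Give MACE with all revascularisation, and death/MI/stroke, as supporting analyses.
5. Count 90-day MACE to a fixed day 90 from one stated time origin, reconciling index PCI in 4(e) with randomisation in the Table 1 footnote.

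The 90-day count should not be cut at the study catheterisation. That would let follow-up vary from day 75 to 105 and drop any MI or stroke caused by the catheterisation, which 4(f)(ii) lists as risks. It could also remove genuine events when a clinically indicated catheterisation takes the place of the study one. All deaths, MIs, strokes and clinically driven procedures stay in, including those at such a substitute catheterisation.

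The cost is revised endpoint wording, one form item, some record retrieval and a little more adjudication. The composite will contain fewer events. These are counting rules and leave patient management unchanged.

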### **Sample Size Determination**

There is only one study which examined the treatment of medication only (20mg Pravastatin or 10mg Simvastatin) vs. LDL-apheresis with statin medication on coronary plaque regression in familial hypercholesterolemia and published in 2002 Journal of American College of Cardiology. The trial reported the net change of plaque area from baseline to one year follow-up. The changes were  $-0.69 \pm 2.08 \text{mm}^2$  in the LDL-apheresis group vs.  $0.88 \pm 1.75 \text{mm}^2$  in the medication only group. Two studies, which have primarily mobilized coronary atheroma LDL using HDL or its apoprotein, have shown similar magnitude of atheroma regression at 6-10 weeks, without directly lowering LDL levels. Given the expected 85% reduction in LDL after LDL-apheresis, we expect to observe a similar treatment effect for the primary effectiveness outcome of this study at 12 weeks.

The sample size of 30 patients for the first feasibility/pilot study leads to a power of 54% with  $\alpha = 0.05$  and the same effect size as reported in the published paper (Cohen's D effect size = 0.82 for  $-0.69 \pm 2.08 \text{mm}^2$  in the LDL-A group vs.  $0.88 \pm 1.75 \text{mm}^2$  in the medication only group). The power decreases to 38% with  $\alpha = 0.05$  and a more meaningful lower Cohen's D effect size of 0.65 by decreasing the difference of two treatment means by 20% ( $-0.38 \pm 2.08 \text{mm}^2$  in the LDL-A group vs.  $0.88 \pm 1.75 \text{mm}^2$  in the medication only group). The power decreases further to 31% by considering 20% drop-out rate with  $\alpha = 0.05$  and the Cohen's D effect size = 0.65.

The second stage of pivotal study is approved to obtain the 90% power to detect a Cohen's D effect size of 0.65 ( $-0.38 \pm 2.08 \text{mm}^2$  in the LDL-A group vs.  $0.88 \pm 1.75 \text{mm}^2$  in the medication only group) with the randomization scheme of 1:1,  $\alpha = 0.05$ , and a 20% drop-out rate, the pivotal study needs a sample size of 128.

## **Baseline Characteristic Comparisons**

Patient characteristics and outcome measures at baseline will be compared between the two treatment groups (ILLT vs. SMT) to determine if the treatment arms differ on any important variables. The chi-square test or Fisher's exact test will be used for categorical variables and the t-test for two independent samples will be used for continuous variables as shown in the following sample table:

Variable	ILLT		SMT		p-value
	N	Mean±SD (or %)	N	Mean±SD (or %)	
Age (yrs)					
Male(%)					

The following data will be summarized using the table format above:

- Demographics
- Clinical Evaluations
- Lab Tests
- Medical History
- Index PCI Results
- Index PCI Complications
- IVUS-VH Chart
- EPC Counts
- Medications Usage – Dosage

